6. ANALYSIS

The statistical methods to be used to compare groups for primary and secondary outcomes and methods for point and interval estimation are summarised below. This includes methods for additional analyses, such as adjusted analyses and subgroup analyses.

The primary estimand of interest will be a treatment policy estimand (ITT population), using data from all randomised participants as randomised. This is chosen as the primary estimand to reflect the pragmatic nature of the study, and to identify the treatment effect regardless of any intercurrent events occurring. The elements of the primary estimand are summarised above in **Table 1**.

The protocol also mandates a per-protocol analysis. The per-protocol analyses (section 4.2) will include all randomised participants who received their allocated treatment but excludes those randomised participants who were found ineligible post-randomisation or did not receive their allocated treatment.

The primary analysis and sensitivity analysis described in sections 6.2-6.4 focus on the primary estimand detailed in **Table 1** which targets the average difference in FIQR scores (ATE) between the two interventions in the combined groups randomised to receive each intervention. The resulting treatment effect represents

the average difference in FIQR scores we can expect if all participants in the target population were treated with dCBT-I instead of being treated with sleep hygiene alone.

A secondary analysis adjusting for compliance with the intervention (complier average causal effect, CACE) will also be performed using instrumental variables approach (Peugh et al. 2017).

6.1 Outcome Definitions

Primary outcome: Fibromyalgia Impact Questionnaire Revised (FIQR): measured pre-randomisation (baseline), 3 months (post-treatment follow-up), and then at 6 months and 12 months. Collected electronically via REDCap survey.

The FIQR is a validated tool based on the revised symptom impact questionnaire (SIQR), widely used in rheumatology, and assesses the impact of fibromyalgia on an individual's daily life(Bennett, Friend, et al. 2009). It includes questions on the following domains: physical functioning, pain intensity and characteristics, fatigue, sleep quality, emotional well-being (mood and anxiety), and impact on work and social interactions. It is measured on a scale from 0 to 100, where higher scores indicate worse quality of life.

Secondary outcomes:

Insomnia severity: Insomnia severity will be measured pre-randomisation (baseline), and at 3-, 6-, and 12months via the REDCap electronic survey tool. The Insomnia Severity Index (ISI) assesses severity of insomnia symptoms and their impact, and is a widely used measure of insomnia severity in both clinical and research settings(Bastien, Vallières, and Morin 2001; Chen, Jan, and Yang 2017). It consists of seven items evaluating different aspects of insomnia, including difficulties with falling asleep, staying asleep, and waking up early; satisfaction with current sleep patterns; interference with daily functioning; quality of life; worry about sleep problems. It may be a more valid measure of sleep quality changes with CBTi compared to the PSQI (see below)(Chen, Jan, and Yang 2017). It is measured on a scale of 0 to 28, where higher scores indicate worse insomnia symptom severity.

Pittsburgh Sleep Quality Index (PSQI): The PSQI will be measured pre-randomisation (baseline), and at 3-, 6-, and 12-months via the REDCap electronic survey tool. The PSQI assesses sleep quality and patterns. It complements the ISI by providing an assessment of sleep quality across seven components: sleep quality, sleep latency, sleep duration, sleep efficiency, sleep disturbance, daytime dysfunction, and use of sleep medications(Buysse et al. 1989).

Observed sleep metrics (actigraphy): Participants will be given an actigraphy device (CamNtech MotionWatch 8) to wear on their wrist for 7 days prior to the baseline (pre-randomisation) and 3-month visits. Alongside this, they will be asked to complete the Consensus Sleep Diary each day(Carney et al. 2012), where they documented sleep times and self-reported sleep quality. The sleep diaries are used to inform the derivation of the observed sleep metrics from actigraphy. Measures derived from actigraphy include total sleep time, time in bed, sleep efficiency, sleep onset latency, and sleep fragmentation.

Pain severity: Pain severity will be measured pre-randomisation (baseline), and at 3-, 6-, and 12-months via the REDCap electronic survey tool. The 36-item short form (SF-36) health survey assesses overall health and wellbeing across eight domains (Framework 1992): physical functioning, role limitations due to physical health, role limitations due to emotional wellbeing, fatigue, emotional wellbeing, social functioning, pain, and general health. In this trial, the Bodily Pain subscale (BPS) is used as a measure of the impact of pain on physical health. It is a composite of two items measuring pain intensity and pain interference, a measure of how much pain interferes with daily activities. Scores for each subscale are transformed to a scale of 0-100, with lower scores representing worse health status.

Subjective cognitive complaints: Cognitive symptoms will be measured pre-randomisation (baseline), and at 3-, 6-, and 12-months via the REDCap electronic survey tool. The British Columbia Cognitive Complaints Inventory (BC-CCI) assesses subjective cognitive complaints through six items assessing self-reported problems over the past seven days with concentration, memory, expressing thoughts, word finding, thinking speed, and problem-solving(Iverson and Lam 2013). Although more typically used in evaluation of patients with mood disorders, this outcome measure was selected for this trial to facilitate comparison with the SPIN trial, which evaluated the effect of dCBT-I on cognitive function in patients with insomnia(Kyle et al. 2020). It is measured on a scale of 0 to 18, where higher scores indicate worse subjective cognitive symptoms.

Cognitive testing: Cognitive testing will be performed at the baseline (pre-randomisation) and posttreatment (3-month) study visits. As one of the principal symptoms of 'fibrofog' is concentration difficulties, a test of sustained visual attention was carried out during the visit(Zhao et al. 2022). This test was selected as previous studies have found deficits in sustained attention in patients with brain-fog symptoms post-COVID, which phenotypically may resemble the cognitive symptoms seen in fibromyalgia(Zhao et al. 2022). This was performed during the visit on an Apple iPad with attached keyboard on a Google Chrome browser. The task involved pressing the spacebar when '0' appeared amidst other digits (1-9), masked by a semitransparent grey checkerboard. Each block lasted 60 seconds, and after a practice block, 9 blocks were performed in total. The hit rate was calculated from correct hits, while false positive rate was calculated from incorrect hits. A composite measure of task accuracy, D', is derived. Reaction time (RT) for correct hits is measured as the time between the digit appearing on the screen and the spacebar being pressed. RT variability is also assessed.

Health-related quality of life: Quality of life will be measured pre-randomisation (baseline), and at 3-, and 6months via the REDCap electronic survey tool. For the planned economic evaluation, the EuroQol-5D-5L (EQ-5D-5L) will be used to estimate quality adjusted life years (QALYs), which are measures on a scale of -0.59 to 1.0, where 1.0 is a full year of perfect health. The adult value set for the UK will be used to estimate QALYs.

Healthcare resource utilisation: healthcare utilisation will be measured pre-randomisation (baseline), and at 3-, and 6-months via the REDCap electronic survey tool. For the planned economic evaluation, participants will report their healthcare service use over the previous 3 months, including hospital visits, medical imaging, and consultations with healthcare professionals (e.g., GPs, nurses, physiotherapists). Information was also collected on medications, unpaid caregiving, social services, and the financial impact of the condition on relatives and friends, including out-of-pocket expenses for care, transportation, and medical treatments.

Magnetic Resonance Imaging (MRI): A neuroimaging sub-study will be nested within the trial, with eligible participants invited to also undergo a brain MRI at the baseline (pre-randomisation) and 3-month study visits. Neuroimaging data will be acquired on a 3T Siemens Prisma MRI scanner at the Oxford Centre for Functional MRI of the Brain (FMRIB) at the John Radcliffe Hospital in Oxford. Participants will complete whole brain structural, resting state BOLD imaging, ASL imaging, and H1-MRS of the posterior insula.

Complications: Adverse events will be measured pre-randomisation (baseline), and at 3-, and 6-months via the REDCap electronic survey tool. Participants will be asked to report any potential adverse events related to dCBT-I, including physical and psychological symptoms such as fatigue, low mood, pain, and difficulty concentrating. The will rated the severity of these symptoms and how much they interfere with normal functioning, on a scale from "Did not experience" to "Very much." Participants will also report incidents of sleepiness over the preceding 3 months, including hospital admissions, accidents, falls, or near-miss incidents, and have the opportunity to mention any other relevant events.

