3. STUDY METHODS

3.1 Trial Design/framework

PainLESS is a single-centre, prospective, randomised, superiority trial using a two-arm parallel group design in a single-centre in Oxford, UK. Adults aged 18 years or older with fibromyalgia and concomitant sleep disturbance, will be randomised in a 1:1 ratio to either receive dCBT-I and sleep hygiene advice, or sleep hygiene advice only. The nature of the treatment means that the participants cannot be blinded to the treatment received; however, the outcome assessors will be blinded to the participant's treatment allocation. This trial was nested within a larger observational cohort. Within the trial, a subgroup of eligible participants underwent a brain MRI at baseline and at 3-months post-randomisation.

The trial includes an internal pilot (phase 1) which was designed to confirm the expected rate of recruitment and feasibility of the study design, and to estimate variability of the outcome measure to inform the sample size for Phase 2. This pilot was planned to include 30 participants. The study investigators will make a decision regarding trial continuation in the event that the recruitment target for the internal pilot is not met. Otherwise, the trial would continue into the main phase (phase 2), and patients from the internal pilot would be included in the final analysis. The main trial phase was planned to be recruiting from Oxford University Hospitals NHS Foundation Trust (OUH) and Connect Health, stratified by sex to account for known imbalances in fibromyalgia prevalence, and by participation in the brain MRI sub-study to ensure a balanced sample for this sub-study. Follow-up was planned to be made in person at 3 months, and electronically (sent by e-mail or text message) for patient reported outcomes at 3 months (primary outcome time-point), 6 months and 12 months.

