6.7 Harms

This is a low risk, pragmatic trial where the intervention, dCBT-I, is in common use. Thus, we do not anticipate many SAEs. All adverse events are submitted to the trial investigators only if they arise within 12 months post-randomisation and they fall under the category of an SAE: events resulting in death; life-threatening; required hospitalisation; prolonged hospitalisation; other important medical event which may require medical or surgical intervention to prevent one of the serious outcomes listed. SAEs potentially related and unexpected are recorded on the trial's database and assessed for seriousness, causality and expectedness (**Table 6**).

Table 6. List of serious adverse events

Allocatio n	Diagnosi s	Timin g of inset of event ¹	Descriptio n of event (including signs & symptoms)	Action taken to deal with the event (including an treatments)	Reason for seriousness 2	Causality: is the event related to the intervention? ³	Expectednes s (in relation to what is known about the intervention) 4

¹ post-randomisation weeks

² Death; Life-threatening; required hospitalisation; prolonged hospitalisation; other important medical event which may require medical or surgical intervention to prevent one of the serious outcomes listed. ³ Possibly related; Probably related; Definitely related

⁴ Expected; Unexpected

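### SAP 6.7 accepts SAEs up to 12 months after randomisation, but participants are asked about adverse events only up to 6 months, so months 6 to 12 have no solicited collection

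*SAP*

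**What the plan says.** The SAP treats harms in two places.

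Section 6.7 sets the window for SAEs: "All adverse events are submitted to the trial investigators only if they arise within 12 months post-randomisation". It adds a filter: "SAEs potentially related and unexpected are recorded on the trial's database and assessed for seriousness, causality and expectedness". The resulting events are listed in Table 6, which has a column for onset in weeks after randomisation.

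Section 6.1, under Complications, sets the enquiry: "Adverse events will be measured pre-randomisation (baseline), and at 3-, and 6-months via the REDCap electronic survey tool". The module asks about symptoms that might be due to dCBT-I. It continues: "Participants will also report incidents of sleepiness over the preceding 3 months, including hospital admissions, accidents, falls, or near-miss incidents". An open item lets participants mention anything else. Resource use is the other survey in which a hospital stay would appear, and its schedule is the same: "healthcare utilisation will be measured pre-randomisation (baseline), and at 3-, and 6-months via the REDCap electronic survey tool". It also looks back three months.

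Other self-reported outcomes run longer. For example: "Pain severity will be measured pre-randomisation (baseline), and at 3-, 6-, and 12-months via the REDCap electronic survey tool". FIQR, ISI, PSQI and BC-CCI follow that schedule as well. Section 3.1 describes one face-to-face follow-up visit, at month 3, with questionnaires delivered "electronically (sent by e-mail or text message) for patient reported outcomes at 3 months (primary outcome time-point), 6 months and 12 months".

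Section 3.5 ends the main analysis at 6 months and leaves the 12-month data to a separate plan. Protocol section 8 defines SAEs and sets out reporting to the ethics committee, but gives neither a time window nor a schedule for asking participants.

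**The concern.** A reader of Table 6 will take it as a 12-month list, because 6.7 says so. Yet no described instrument asks participants about harm in the second half of that period. Few or no entries with onset after month 6 could mean that nothing happened, or that nobody asked, and the table gives no way to tell which.

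The gap does not follow from an end to contact. Participants receive a REDCap survey at 12 months on fibromyalgia impact, insomnia, sleep quality, pain and cognition. The harms items are simply not named as part of it. The trial also has no data monitoring committee (SAP 3.4), so no such body would raise the question during the trial.

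**Working it through.** The plan states no figure that depends on this schedule, so there is none to reproduce. The check is one of coverage.

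**Inputs**

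- SAE window: W = 12 months from randomisation (SAP 6.7).
- Solicited enquiry after randomisation: t = 3 and 6 months (SAP 6.1). The baseline survey precedes randomisation and contributes nothing to the window.
- Recall: R = 3 months, stated for the incident items and for healthcare use. No recall period is stated for the symptom items.

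**Coverage as planned.** Each survey covers the interval from t − R to t.

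- 3-month survey: months 0 to 3.
- 6-month survey: months 3 to 6.
- Covered: 6 months, 6/12 = 50%.
- Open: 12 − 6 = 6 months, namely months 6 to 12.

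Two robustness points follow. First, two surveys with a 3-month recall cover at most 2 × 3 = 6 months, whatever day they are completed, so 50% is the ceiling for the incident items. Second, a longer recall for the symptom items would not help, because a survey at month 6 cannot reach forward.

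**Coverage under alternatives**

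| Surveys (months) | Recall | Covered | Open |
|---|---|---|---|
| 3, 6 (as planned) | 3 months | 6/12 (50%) | months 6–12 |
| 3, 6, 12 | 3 months throughout | 9/12 (75%) | months 6–9 |
| 3, 6, 12 | 3 months at 3 and 6; since the 6-month survey at 12 | 12/12 | none |
| 3, 6, 9, 12 | 3 months throughout | 12/12 | none |

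Repeating the module unchanged at 12 months would thus close only half of the gap.

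**Number of events.** The expected number of missed entries is the person-time in months 6 to 12, multiplied by the SAE rate, the share that is both potentially related and unexpected, and the share not volunteered. The documents give none of the last three, so no count is offered.

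**The case against.** The strongest reply is that the two sections do different jobs. The module in 6.1 is a tolerability outcome: it asks about symptoms that may be due to dCBT-I and about incidents of sleepiness. Section 6.7 is an event-driven process with an outer time limit, and such a limit does not promise active enquiry throughout. This stands in part. The two windows do not strictly contradict each other, and SAEs can be reported at any time. It does not remove the gap in solicited collection, because the documents describe no other route by which the trial asks about harm.

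Second, trial participants are nested in the cohort. Protocol section 5 gives a wait of about 6 months before pain rehabilitation, and section 7.5 times later visits from the start of therapy, each with an update of medical history. Some of these visits may fall in months 6 to 12 after randomisation. That is a fair point, and it means incidental capture is possible. But the visits do not name adverse events, are not timed from randomisation, and are not described as SAE collection.

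Third, section 3.5 ends this SAP's main analysis at 6 months, and over that period solicited enquiry is scheduled in full. This also stands, and it limits the consequence. Section 6.7 nevertheless states 12 months, so the two need reconciling.

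A reader might go further and infer that a handful of SAEs will be lost, by applying an assumed rate to the 78 participants. The documents give no rate, and only potentially related and unexpected SAEs are recorded, so that count has no basis. A reader might also infer that unblinded Sleepio users will volunteer events more readily than controls. Participants are indeed unblinded, but nothing in the documents shows differential reporting; it is a possibility only.

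**Conclusion.** The point holds as a gap in solicited harms collection: 6 of the 12 months in the stated SAE window, months 6 to 12, have no scheduled question about adverse events or hospital use. The 50% rests on the survey times and window as written in the SAP. The 3-month recall matters for the choice of remedy, and is stated only for the incident and healthcare-use items.

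The effect on the primary result and on the 6-month safety summary is nil. What is affected is the interpretation of Table 6 beyond month 6, and the later 12-month report. The documents do not support saying that SAEs in months 6 to 12 cannot be captured, or that any particular number will be missed. This is an inconsistency in harms reporting that is cheap to repair and worth repairing.

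**What to change.** **Participants not yet at 12 months.** Add the existing adverse-event module to the 12-month REDCap survey. Word its incident item to cover the time since the 6-month survey. Leave the 3- and 6-month wording alone, so that recall periods are not mixed at time points already collected.

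**Cross-check.** Compare hospital admissions reported in the adverse-event and healthcare-use surveys with the SAE list. An admission missing from Table 6 may be properly absent, because of the relatedness and expectedness filter. The check should therefore confirm that the assessment was made.

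**Participants already past 12 months.** SAP version 1.1 is dated 29 April 2025 and the protocol's planned study period ends on 30 April 2025, so this may be many or all of them; the documents do not say. For them, state in 6.7 and in Table 6 that solicited collection ended at 6 months, and list SAEs from months 6 to 12 separately as spontaneous reports. The onset column in Table 6 already allows the split.

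**Text.** Reconcile the 12-month window in 6.7 with the 6-month reporting horizon in 3.5, for example by saying which report will carry SAEs with onset after month 6.

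The cost is a few more minutes of questionnaire time at 12 months, one data cross-check, and a small amendment, with approval where it is needed (protocol 12.4). The disclosure for participants past 12 months needs no new data.

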6.2 Analysis Methods

Analysis of Primary Estimand (ATE): A Treatment Policy Analysis

Unadjusted summary statistics of the FIQR scores will be displayed by treatment allocation using means and standard deviations at each assessment point. The primary analysis will be conducted using **Constrained Longitudinal Data Analysis (cLDA)**(Lu 2010). This model includes baseline FIQR as part of the response vector while constraining baseline means to be identical across treatment groups, ensuring that differences in FIQR post-randomisation reflect true treatment effects rather than baseline imbalance. This method offers advantages over traditional mixed-effects models (LMM) and ANCOVA by providing a more efficient and unbiased estimate of treatment effects while maintaining the interpretability of a baseline-adjusted analysis(Coffman, Edelman, and Woolson 2016; Lu 2010).

A linear mixed-effects model (LMM) with constraints will be used to compare FIQR scores between treatment groups across all available time points (baseline, 3-months, 6-months, and 12-months), ensuring that baseline differences are accounted for without requiring explicit adjustment in the fixed effects. The model will include a fixed effect for treatment group, time (categorical), and their interaction to allow for non-parallel treatment effects over time. To account for repeated measures within individuals, a random intercept will be specified for each participant, and an unstructured covariance structure will be assumed for residual errors to allow for flexible correlation between repeated measurements.

The constrained longitudinal model will be specified as:

$$Y_{i,t} = \mu + \gamma_t Time_t + \delta_t (Treatment_i \times Time_t) + \sum_k \beta_k Covariate_{k,i} + u_i + \varepsilon_{i,t}$$

where:

- *Y_{i,t}* is the FIQR score for participant *i* at time *t*
- μ is the grand mean FIQR score at baseline, constrained to be equal for both treatment groups
- $\gamma_t Time_t$ is the fixed effect of time (categorical), with baseline as the reference category
- δ_t is the interaction effect between treatment and time, estimating the treatment effect at each follow-up time point
- β_k represents covariate adjustment terms for stratification factors (sex, participation in the MRI substudy)
- $u_i \sim N(0, \sigma_u^2)$ represents the random intercept for participant i
- $\varepsilon_{i,t} \sim N(0, \sigma_t^2)$ is the residual error term

A random intercept model with an unstructured covariance structure will be used to account for withinsubject correlation. Adjusted mean differences at 3 months (primary endpoint), 6 months, and 12 months will be presented with 95% confidence intervals and p-values.

Secondary analysis: As a secondary analysis, the above model will be run including a set of *a priori* baseline covariables which may predict the outcome or missingness. In addition to the stratification factors (sex, participation in the MRI sub-study), these will include age, depression (PHQ-9), and anxiety (GAD-7).

Secondary outcome measures: The same methods outlined above will be used to examine the following secondary outcome measures: subjective cognition (British Columbia Cognitive Complaints Inventory, BC-CCI); objective cognitive performance (performance on the number vigilance task: sensitivity, reaction time, reaction time variability); self-reported sleep quality (insomnia severity index, ISI; Pittsburgh Sleep Quality Inventory, PSQI); observed sleep measures derived from actigraphy (sleep efficiency, sleep fragmentation, total sleep time, wake after sleep onset); and pain (Short Form 36 Bodily Pain Scale, SF36-BPS). All outcome contain measurements at baseline (pre-randomisation), 3-months, 6-months, and 12-months, with the exception of actigraphy and objective cognitive performance which were measured at baseline and 3-months.

Model checking and normalising transformations: Assumptions of normality will be assessed graphically looking at residual and quantile-quantile (QQ) plots, and data transformation will be considered if model assumptions (particularly normality of residuals) are clearly violated. Mixed-effects models are robust to small deviations from normality in the residuals; however, if approximate normality cannot be achieved, data normalising transformations will be considered prior to proceeding to fit the same mixed effects linear model described above on the transformed scale.

Examination of residuals following model fitting will be undertaken including exploration of dependencies with observed covariates. Consideration will be given to augmenting the model to heteroscedastic (level 1) residuals especially when the model is fitted in the original scale, where strong patterns are observed between residual errors and covariates and variance increases with the mean(Goldstein 2005). Comparison of the log-likelihood values of a small number of competing models will be used to decide which model to select (higher log-likelihood values indicate a better fitting model).

